SUMMARY OF CHANGES - Protocol

NCI Protocol # 8348

Local Protocol # 09-293

Current Protocol Version Date: January 03, 2019

Previous Protocol Version Date: July 30, 2018

#	Section	Page(s)	Change
1.	Header; Title Page	All; 1	The protocol version date has been updated from July 30, 2018 to January 03, 2019.
2.	Title Page	2	The Site PIs for University of Michigan and Evanston Hospital/NorthShore University Health System have been updated.
3.	6.1.1	40-43	
Revision of the Protocol CAEPR:
 
 • Added New Risk: 
 • Rare but Serious: Hemolytic uremic syndrome; Thrombotic thrombocytopenic purpura • Increase in Risk Attribution: 
 • Changed to Rare but Serious from Also Reported on Cediranib Trials But With Insufficient Evidence for Attribution: Heart failure; Hepatic failure; Nephrotic syndrome; Wound complication
4.	ICF – Ph 1	12	
Revision of the ICD as Specified Below: The condensed risk profile has been modified
 
 • Added New Risk: 
 • Rare: Anemia, kidney problems which may cause tiredness, bruising, swelling, or may require dialysis • Increase in Risk Attribution 
 • Changed to Rare from Also Reported on Cediranib Trials But With Insufficient Evidence for Attribution (i.e., added to Risk Profile): Liver damage which may cause yellowing of eyes and skin, swelling; Non-healing surgical site • Provided Further Clarification: 
 • Blood clot which may cause swelling, pain, shortness of breath (under Occasional) is now reported as Blood clot which may cause swelling, pain, shortness of breath, confusion, or paralysis (under Occasional)

#	Section	Page(s)	Change

1. SCHEMA

Phase I Dose Escalation Scheme

Dose escalation will proceed within each cohort according to the following scheme:	
Number of Participants with DLT at a Given Dose Level	Escalation Decision Rule
0 out of 3	Enter 3 participants at the next dose level.
≥ 2	Dose escalation will be stopped. This dose level will be declared the maximally administered dose (highest dose administered). Three (3) additional participants will be entered at the next lowest dose level if only 3 participants were treated previously at that dose.
1 out of 3	Enter at least 3 more participants at this dose level. 
 • If 0 of these 3 participants experience DLT, proceed to the next dose level. • If 1 or more of this group suffer DLT, then dose escalation is stopped, and this dose is declared the maximally administered dose. Three (3) additional participants will be entered at the next lowest dose level if only 3 participants were treated previously at that dose.
≤ 1 out of 6 at highest dose level below the maximally administered dose	This is generally the recommended phase II dose. At least 6 participants must be entered at the recommended phase II dose.

[figure not shown]
Phase II Component at Recommended Phase 2 Dose (RP2D)

** prior to initiation of treatment, patients will be recruited to the Medical Oncology Branch of the Center for Cancer Research, National Cancer Institute for translational component of study, see schema below.

Translational Sample Acquisition Schema

Schema for sample acquisition for translational objectives for patients at NCI participating in this component:

At Progression

[figure not shown]

TABLE OF CONTENTS

SCHEMA	5
1. OBJECTIVES	11
1.1. Study Design.....	11
1.2. Primary Objectives.....	11
1.3. Secondary Objectives.....	11
2. BACKGROUND	12
2.1. Ovarian Cancer.....	12
2.2. Study Agents.....	14
2.2.1. Cediranib.....	14
2.2.2. Olaparib.....	19
2.3. Background for Correlative Studies.....	20
2.4. Rationale.....	22
3. PARTICIPANT SELECTION	24
3.1. Inclusion Criteria.....	24
3.2. Exclusion Criteria.....	27
3.3. Inclusion of Women, Minorities and Other Underrepresented Populations.....	29
4. REGISTRATION PROCEDURES	30
4.1. General Guidelines for DF/HCC and DF/PCC Institutions.....	30
4.2. Registration Process for DF/HCC and DF/PCC Institutions.....	30
4.3. Registration Process for non DF/HCC Institutions.....	31
5. TREATMENT PLAN	31
5.1. Pre-treatment Criteria.....	33
5.2. Agent Administration.....	35

1. OBJECTIVES

1.1. Study Design

This is a Phase I/II trial of the combination of cediranib and olaparib in the treatment of recurrent ovarian, fallopian tube, or peritoneal cancer or in recurrent triple-negative breast cancer to define the safe dose of this combination, followed by a randomized two-arm Phase II study comparing the combination of cediranib and olaparib at the recommended Phase 2 dose (RP2D) as determined in the Phase I portion of the study compared to the control arm of olaparib alone in patients with recurrent platinum-sensitive papillary-serous or endometrioid ovarian, fallopian tube, or peritoneal cancer. A total of up to 148 patients are planned for study enrollment, with up to 28 patients in the phase I dose escalation portion, up to 90 patients in the Phase II randomized portion, and up to 30 patients in the phase I (tablet) dose escalation portion.

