5. TREATMENT PLAN

Treatment will be administered on an outpatient basis. Expected toxicities and potential risks as well as dose modifications for cediranib and olaparib are described in Section 6 (Expected Toxicities and Dosing Delays/Dose Modifications). No investigational or commercial agents or therapies other than those described below may be administered with the intent to treat the participant's malignancy.

Phase I

Each cycle will be 28 days (4 weeks). For the Phase I component of this study, treatment cohorts will consist of 3 to 6 patients and the dose escalation schedule will be as follows. Participants enrolled to the Phase I portion of the study will continue treatment with olaparib capsule formulation.

	Dose Level	Cediranib	Olaparib (capsule)
	-1	15mg PO daily	100mg PO BID
Starting dose →	0	20mg PO daily	100mg PO BID
	1	20mg PO daily	200mg PO BID
	2	30mg PO daily	200mg PO BID
	3	30mg PO daily	400mg PO BID

Phase I-T

For the Phase I-T component of this study, treatment cohorts will consist of 3 to 6 patients. Two separate cohorts of dose escalation will be accrued, one with a dosing of cediranib at 30mg daily (Phase I-TA) and a second at cediranib dosing of 20mg daily (Phase I-TB). The two Phase I-T

dose escalation schemes will enroll in parallel. Participants enrolled to the Phase I-T portion of the study will receive treatment with the olaparib tablet formulation. The dose escalation schedule for the two cohorts will be per the following tables. If the cohort of patients enrolled in a given dose level completes the DLT assessment window without experiencing a DLT in the first three patients or with 1 or fewer DLTs in six patients, the next higher dose level may be assessed.

Phase 1-TA Dose Escalation: Cediranib 30mg

	Dose Level	Cediranib	Olaparib (tablet)
	-1-TA	30mg PO daily	100mg PO BID
Starting dose →	0-TA	30mg PO daily	150mg PO BID
	1-TA	30mg PO daily	200mg PO BID
	2-TA	30mg PO daily	250mg PO BID
	3-TA	30mg PO daily	300mg PO BID

Phase 1-TB Dose Escalation: Cediranib 20mg

	Dose Level	Cediranib	Olaparib (tablet)
	-1-TB	20mg PO daily	150mg PO BID
Starting dose →	0-TB	20mg PO daily	200mg PO BID
	1-TB	20mg PO daily	250mg PO BID
	2-TB	20mg PO daily	300mg PO BID

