Toxicity assessments will be done using NCI Common Terminology Criteria for Adverse Events (CTCAE v4.0). CTCAE v4.0 is identified and located on the CTEP website at (http://ctep.cancer.gov/protocolDevelopment/electronic_applications/ctc.htm). Dose escalation to the next dose level will occur when the preceding cohort reaches the end of Cycle 1. Patients who do not complete both treatments in cycle 1 for reasons other than cediranib or olaparib toxicity will be replaced. Toxicity data for each cohort will be reviewed prior to dose escalation. Intra-patient dose escalation will be allowed at the discretion of the investigator and overall trial PI for patients following their completion of Cycle 2 if the following criteria are met: the patient had no > grade 1 toxicities secondary to study treatment except for grade 2 or 3 HTN or nausea no greater than grade 1 after treatment with concurrent medications, the subsequent dose cohort has completed Cycle 1, and evaluation of DLTs has been completed for the subsequent dose cohort and the dose was deemed to be safe due to ≤ grade 2 toxicities. Dose escalation will occur for both cediranib and olaparib according to the dose escalation schema. Patients can be dose-escalated multiple times as long as they continue to meet criteria and do not exceed the final protocol-specified dose level (dose Level 3). All intra-patient dose escalations must be discussed and approved by the overall trial PI. If treatment-related toxicities related to one of the study drugs restricts further escalation of that drug, a modification to the dose escalation schema may be considered.

Phase I-T PK expansion

Once the MTD has been established during the Phase 1-T, two PK expansion cohorts of 6 evaluable patients each will be enrolled for pharmacokinetic studies. Participants in this expansion will receive a one week of either single-agent cediranib (Cohort 1-T PKced) or single-

agent olaparib (tablet formulation; Cohort 1-T PKolap) prior to starting cycle 1 of combination cediranib and olaparib (tablet formulation). Full details of the PK evaluation schedule are outlined in Section 8.14. Participants must be able to continue on study drug without any dose holds through Cycle 1 Day 16 of treatment to be considered fully evaluable for PK studies.

Participants participating in the PK expansion cohorts will take their study drugs on the following schedule once combination dosing has started:

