1. Cediranib tablet(s) in the morning on an empty stomach (at least 2 hours after eating)
2. Light meal ~1 hour after taking cediranib
3. Morning olaparib tablet(s) after light meal
4. Evening olaparib tablet(s) 12 hours after morning olaparib dose, taken after a light meal

Phase II

For the Phase 2 portion of this study, patients will be randomized in 1:1 ratio to one of the two following arms:

1. Olaparib 400mg BID (capsule)
2. Cediranib and olaparib at the RP2D (cediranib 30mg daily and olaparib 200mg BID (capsule)) derived from the Phase I portion of this study

Participants enrolled to the Phase II portion of the study will continue treatment with olaparib capsule formulation.

All patients must meet the eligibility criteria for the Phase II portion of the study, as outlined in Section 3. Patient randomization will be stratified based upon:

1. Prior receipt of anti-angiogenic therapy.
2. BRCA mutation status (carrier, non-carrier, unknown).

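### Section 1.1 does not say whether the 30 Phase I-T places include the 12 PK patients, and neither reading matches the design

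*Combined protocol and SAP*

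**What the plan says.** Section 1.1 gives the overall limit, "A total of up to 148 patients are planned for study enrollment", and splits it into three parts: "up to 28 patients in the phase I dose escalation portion", 90 in the randomized Phase II, "and up to 30 patients in the phase I (tablet) dose escalation portion". It has no line for pharmacokinetics.

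Section 5 describes Phase I-T as two escalations run in parallel: "Two separate cohorts of dose escalation will be accrued, one with a dosing of cediranib at 30mg daily" (Phase I-TA) and the other at 20 mg (Phase I-TB). From its starting level upward, Phase I-TA has four levels and Phase I-TB has three. Cohorts are 3 to 6 patients, and Section 5.3 requires at least 6 at the MTD.

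Once the Phase I-T MTD is established, "two PK expansion cohorts of 6 evaluable patients each will be enrolled for pharmacokinetic studies". Sections 8.14 and 14.1.3 repeat the 12. Section 5 adds: "Participants in this expansion will receive a one week of either single-agent cediranib", or single-agent olaparib, before cycle 1. It also sets a replacement rule: "Patients who do not complete both treatments in cycle 1 for reasons other than cediranib or olaparib toxicity will be replaced".

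Section 14.2 says the sample size varies with Phase I and Phase I-T accrual. It fixes 90 for Phase II and gives no number for Phase I-T or for PK.

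**The concern.** The three figures in 1.1 use up the whole 148, yet the design has a further group of 12. They cannot be patients already treated in the escalation: they enter after the MTD is confirmed, and each starts with a week on one drug alone. Either they sit outside the 30 and the total is too small for its parts, or they sit inside it and the 30 must cover two escalations as well.

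If they are inside, two Phase I-T aims draw on the same places: finding the MTD with the tablet (objective 1.2.3) and describing the PK of the combination (objective 1.3.4). The documents do not say which has first call.

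**Working it through.** **Inputs.** Section 1.1: 148, 28, 90, 30. Sections 5, 8.14 and 14.1.3: PK 2×6 = 12. Section 5 dose tables: four Phase I-TA levels and three Phase I-TB levels from the start upward. Section 5.3: 3 patients per level, expanded to 6 after one DLT; escalation stops at two or more; at least 6 at the MTD.

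**The plan's own figure.** 28+90+30 = 148. The sum is correct and leaves no place unassigned.

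**Reading A: PK is outside the 30.** The component ceilings sum to 28+90+30+12 = 160, which is 12 above the stated total. With the other ceilings filled, 148 would hold only if Phase I used at most 148−90−30−12 = 16 of its 28 places.

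**Reading B: PK is inside the 30.** Places left for escalation: 30−12 = 18.

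- No DLT anywhere: Phase I-TA uses 3+3+3+6 = 15 and Phase I-TB uses 3+3+6 = 12, together 27. With PK this is 27+12 = 39, or 9 over.
- Fewest patients for a scheme to declare an MTD, in full cohorts of 3: six at the MTD plus one cohort of three at a level that stopped escalation, 6+3 = 9. Both schemes plus PK: 9+9+12 = 30, with nothing spare. A full enumeration of the 3+3 paths found no other pair in which both schemes declare an MTD within 18.
- One scheme ends with no MTD after 6 patients (two DLTs at the start level and two at the level below): the other may use 12, and 6+12+12 = 30.
- Each scheme stops a cohort at its second DLT, before a third patient enters: 8+8+12 = 28.

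All of these are before replacements. PK evaluability also requires no dose hold through Cycle 1 Day 16, so more than 12 may have to be enrolled to obtain 12.

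**What runs short under Reading B.** If both escalations finish first with no DLT, 30−27 = 3 places remain for 12 PK patients. If instead the PK cohorts are filled once Phase I-TA has run to its top level without a DLT, 15+12 = 27 leaves 3 of the 30 for the whole of Phase I-TB, against its minimum of 9.

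**The case against.** The strongest reply is that these are planning limits and the label is loose. The Phase I figure of 28 carries the same escalation label, although Section 14.1.3 allows up to 8 more patients at the Phase I MTD, so the 30 may likewise be meant to include its expansion. This stands as far as it goes: a reader might infer that the PK patients are counted nowhere, and the text does not establish that. But the looser reading does not rescue the number. The 28 covers Phase I with no DLT plus its expansion (15+8 = 23), though not six at every level plus expansion (24+8 = 32). The 30 does not cover even the no-DLT Phase I-T counterpart, 39.

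It is also fair to say that 30 can be met without the shortest path in both schemes. The documents speak of the MTD in the singular and do not require a cohort to be completed after its second DLT. The two exceptions worked above therefore stand, and a shortfall in Phase I-TB would not by itself defeat objective 1.2.3 once Phase I-TA had an MTD. Both exceptions, however, depend on toxicity appearing early; a well-tolerated course does not fit.

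The statement in 14.2 that the size will vary does not settle the matter, because it supplies no Phase I-T figure.

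A reader might also take the doses named in 8.14 to mean that the Phase I-TA MTD is level 1-TA. The same doses are the capsule RP2D in Section 5, so no count can rest on that.

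**Conclusion.** The stated Phase I-T size and the Phase I-T design do not agree on either reading. The gap is 12 places in the total (160 against 148) if PK is separate, or 9 places on the no-DLT path (39 against 30) if PK is included. The second figure assumes 3 per level, 6 at the top level and no replacements. It is a requirement for that path and not a maximum: one cohort expanded below the top level that then escalates adds 3.

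A reader might infer that the trial would exceed 148. The documents do not show this. The components are ceilings, and Section 5 gives the Phase II combination dose as "derived from the Phase I portion of this study", so Phase I enrolment may already be known and may be below 28. The Phase II sample size, event target and power are unaffected. This is a wrong or undefined stated sample size for one component, and it is worth correcting because the correction is cheap.

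**What to change.** State in 1.1 whether the 30 includes the PK cohorts and, likewise, whether the 28 includes the optional 8. Then restate the Phase I-T figure and the total in both 1.1 and 14.2:

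- PK included: at least 39 for Phase I-T, with an allowance for replacements and expanded cohorts. Before that allowance the ceilings sum to 28+90+39 = 157.
- PK separate: a line of its own for 12 PK-evaluable patients, and component ceilings of 160.

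In either case use actual Phase I enrolment in place of 28 if it is known. The escalation rules and the PK design stay as they are.

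The cost is one clarifying sentence and two or three figures. A higher stated ceiling would need an amendment; Appendix G, Section 5.4, lists a change in sample size or accrual among its examples of major amendments.

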1.2. Primary Objectives

- 1.2.1. Phase 1 Portion:** Assess the MTD of cediranib in combination with olaparib in the treatment of recurrent ovarian, fallopian tube, or peritoneal cancer or metastatic triple-negative breast cancer.
- 1.2.2. Phase 2 Portion:** Assess the efficacy (as measured by progression-free survival (PFS)) of the combination of cediranib and olaparib compared to olaparib alone in recurrent grade 2 or 3 platinum-sensitive papillary-serous or endometrioid ovarian, fallopian tube, or peritoneal cancer.
- 1.2.3. Phase 1-T (olaparib tablet) Portion:** Assess the MTD of cediranib in combination with olaparib tablet formulation in the treatment of recurrent ovarian, fallopian tube, or peritoneal cancer.

1.3. Secondary Objectives

- 1.3.1. Phase 1 Portion:** Assess the toxicities of the combination of cediranib and olaparib in the treatment of recurrent ovarian, fallopian tube, or peritoneal cancer or metastatic triple-negative breast cancer. Assess clinical benefit, progression-free survival, and overall survival for patients treated with cediranib and olaparib.
- 1.3.2. Phase 2 Portion:** Assess tumor response, clinical response benefit (response or stable disease as defined by RECIST response criteria x 16 weeks), and overall survival (OS) for patients treated with cediranib and olaparib at the RP2D as compared with patients receiving olaparib alone.
- 1.3.3. Phase 2 Portion Translational Objectives:**
 - To evaluate the prognostic and predictive role of measured changes in functional vascular imaging using DCE-MRI between pre-study and day 3.

- To evaluate in an exploratory fashion the predictive or prognostic value of SNPs in key genes involved in angiogenesis and DNA repair.
- To evaluate the predictive value of baseline PBMC PAR incorporation on response to therapy.
- To measure early changes in vascular cytokine production and evaluate in an exploratory fashion that these changes may be predictive or prognostic, or differentially affected by the combination of agents.
- To evaluate early changes to circulating endothelial cells and if these changes are predictive or prognostic.
- To assess changes in measures of DNA damage and repair and angiogenesis in tumor cells (tissue and/or malignant effusions) and correlate to drug/drug/combination.

1.3.4. Phase 1-T (olaparib tablet) Portion: Assess the toxicities of the combination of cediranib and olaparib (tablet formulation) in the treatment of recurrent ovarian, fallopian tube, or peritoneal cancer. Assess clinical benefit, progression-free survival, and overall survival for patients treated with cediranib and olaparib (tablet formulation). Assess the pharmacokinetic profile of cediranib and olaparib (tablet formulation) when administered in combination.

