5.1.4. Pre-Cycle 1 Therapy: Translational Component

- All patients will be *strongly* encouraged to participate in the translational component of the trial. Travel to and from the NCI and all costs of imaging, blood draws, biopsy, or fluid sampling done at the NCI will be provided in kind. A stipend to assist with cost of the local stay during this aspect of the trial will be provided, or the patient can elect hospital admission at no cost.
- Biopsiability will be determined prior to scheduling the NCI visit using most recent tumor imaging. This will be followed by an on-study chest/abdominal/pelvic CT with oral and IV contrast obtained the day of evaluation at NCI. A copy of this scan will be provided to the home institution for use in subsequent tumor measurements.
- Patients will be seen at NCI with a copy of their signed protocol consent from their home institution.
- Drug therapy will be initiated after acquisition of initial translational components and dispensed for the 28-day cycle.
- Translational component sample acquisition will occur:
 - Prior to starting therapy
 - Prior to day 3: 2-8 hours after the 5th dose of olaparib (d1 will start with the am dose) and the 3rd dose of cediranib (the first dose of cediranib will be administered at the same time as the first dose of olaparib).

Process	Pre-treatment	Day 3
Blood for PBMCs, DNA, and CECs	X	X
Plasma and serum for cytokines	X	X
DCE-MRI imaging	X	X
Biopsy: core of tumor, involved skin, or malignant effusion sampling	X	X

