8.2. Rationale for Selected Endpoints

These endpoints were selected to allow illustration of mechanism of the agents and potential interaction between the agents. They were also selected to investigate, in an exploratory fashion, whether any measures were predictive or prognostic, with the former being of greater interest.

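### Day-3 changes in DCE-MRI, cytokines and circulating endothelial cells are labelled predictive, but a change that follows randomisation and dosing cannot establish who benefits from adding cediranib; the pre-treatment values already collected can address that question

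*Combined protocol and SAP*

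**What the plan says.** Section 1.3.3 lists the Phase 2 translational objectives. One is "To evaluate the prognostic and predictive role of measured changes in functional vascular imaging using DCE-MRI between pre-study and day 3". Another is "To evaluate early changes to circulating endothelial cells and if these changes are predictive or prognostic". The cytokine objective is marked exploratory. It asks whether early changes are predictive or prognostic, and also whether the combination affects them differently. By contrast, the PAR objective in the same list rests on a pre-treatment value: "To evaluate the predictive value of baseline PBMC PAR incorporation on response to therapy".

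Section 8.2 describes the translational work as exploratory and asks "whether any measures were predictive or prognostic, with the former being of greater interest".

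In Section 5 (Phase II), "patients will be randomized in 1:1 ratio to one of the two following arms": olaparib alone, or cediranib with olaparib. Section 5.1.4 times the second sample "2-8 hours after the 5th dose of olaparib (d1 will start with the am dose) and the 3rd dose of cediranib". The first sample precedes any drug: "Drug therapy will be initiated after acquisition of initial translational components and dispensed for the 28-day cycle". The table in 5.1.4 marks DCE-MRI, blood for CEC, and plasma and serum for cytokines at both time points. Section 8.4 treats Ktrans and kep as continuous outcome variables and expects change through reduced angiogenesis.

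Section 14 gives no model, test or sample size for any translational objective and does not define predictive.

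**The concern.** In a two-arm randomised trial, a marker is usually called predictive when the treatment effect differs by its level. Section 8.2 keeps predictive apart from prognostic and prefers the former, which invites that reading. Randomisation supports such a claim only for a value that treatment has not touched. A day-3 change is itself a response to the assigned regimen. Patients with a given fall in Ktrans on cediranib plus olaparib are not comparable with patients showing the same fall on olaparib alone, because different processes produced the two falls.

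A pharmacodynamic or prognostic signal confined to the cediranib arm could then be presented as a means of selecting patients for the combination. Comparing the change itself between arms is not in question; that comparison is randomised and valid.

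**Working it through.** **Plan figures.** No figure in the plan relates to these objectives. The simulations borrow the Phase II PFS assumptions of section 14.2, so those are reproduced first.

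- Medians of 6 and 10.5 months give HR = 6/10.5 = 0.5714; the plan states 0.5716.
- Schoenfeld events, 1:1 allocation, one-sided alpha 0.10, power 86%: 4(1.2816 + 1.0803)²/(ln 0.5716)² = 4 × 5.578/0.3128 = 71.3, rounded up to 72. The plan's 71 events give 85.9% power, so the figure is reproduced. Sidedness is not stated; the one-sided reading is the one that fits.

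**Why the interaction can be spurious.** Let A be arm (1 = combination), U a latent prognostic factor (SD 1), and M the day-3 change.

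- Hazard: log h = constant + A·ln(HR) + γU. The treatment HR is the same at every U, so no marker is predictive.
- Change: M = shift·A + r_A·U + noise, where r_A is the correlation of M with U in arm A.
- Within an arm, E[U | M] = r_A × (M − arm mean), so the slope of log hazard on M is roughly γ·r_A.
- The arm-by-change coefficient is therefore roughly γ(r₁ − r₀), which is zero only if the correlations are equal.

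A pre-treatment marker cannot have been altered by the drug, so its expected correlation with U is the same in both arms and this term vanishes.

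Approximate spurious interaction HRs with r₀ = 0:

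- r₁ = 0.5, γ = 0.7: exp(0.35) = 1.42
- r₁ = 0.7, γ = 0.7: exp(0.49) = 1.63
- r₁ = 0.7, γ = 1.0: exp(0.70) = 2.01

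**Simulation 1.** 1,500 trials per cell, exponential PFS, control median 6 months, HR 0.5716, 18-month accrual, analysis at month 30. The change correlates 0.5-0.8 with U in the combination arm and is pure noise in the olaparib arm; γ is 0.5 or 0.7. Rejection of the arm-by-change term at 0.05 in three such settings:

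| Patients | Setting 1 | Setting 2 | Setting 3 |
|---|---|---|---|
| 40 | 11.3% | 16.1% | 27.1% |
| 60 | 14.0% | 22.9% | 38.0% |
| 82 | 15.1% | 29.8% | 48.2% |

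With zero correlation the rate was 6.1-6.6%. A repeat run gave 11-26%, 13-38% and 15-48%, with 6-8% at zero correlation.

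**Simulation 2.** 1,000 trials per cell, control median 6 months, HR 6/10.5, censoring uniform over 12-30 months, two-sided 0.05. A pre-treatment marker correlated 0.7 with U in both arms was tested alongside. Entries are for n = 30 / 60 / 90.

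| r₁ | r₀ | γ | Arm × change rejects | Arm × baseline rejects | Median HR, arm × change |
|---|---|---|---|---|---|
| 0 | 0 | 0.7 | 7.3 / 5.6 / 6.0% | 7.5 / 4.7 / 5.9% | 1.00 / 1.01 / 1.00 |
| 0.5 | 0 | 0.7 | 13.9 / 15.8 / 22.9% | 6.2 / 4.7 / 4.8% | 1.39 / 1.34 / 1.35 |
| 0.7 | 0 | 0.7 | 16.6 / 27.2 / 41.2% | 6.7 / 6.4 / 6.2% | 1.65 / 1.54 / 1.57 |
| 0.7 | 0 | 1.0 | 26.3 / 42.9 / 57.8% | 6.3 / 6.6 / 6.1% | 1.93 / 1.79 / 1.76 |
| 0.5 | 0.5 | 0.7 | 7.4 / 6.7 / 6.0% | 6.7 / 6.4 / 6.7% | 1.01 / 1.02 / 1.00 |

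Monte Carlo standard error near 5% is √(0.05 × 0.95/1000) = 0.7 percentage points. The slight excess over 5% in null cells reflects this and small-sample Wald inflation. The simulated HRs follow the approximation, somewhat attenuated.

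The correlations, γ and subset sizes are assumptions. Participation is optional (section 9.2, note o) and its expected number is not stated.

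**The case against.** The strongest reply is that the plan contains no arm-by-change test. That is correct: neither section 8 nor section 14 states one. A reader might infer from section 1.3.3 that a faulty interaction analysis has been prespecified; the documents do not support that. What they contain is an objective without an analysis.

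Second, the protocol also uses predictive loosely, for forecasting response in treated patients: sections 2.3.2 and 2.3.3 do so for cytokines and PAR, and 2.3.1 presents DCE-MRI as a possible early sign of treatment effect. On that reading a day-3 change is a coherent early indicator, analysable within arm. This stands, but it moves the problem to the label: such a result is a pharmacodynamic or prognostic association, and section 8.2 distinguishes the terms.

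Third, a reader might infer that the question the protocol ranks highest goes unanswered. It does not. Section 8.2 names mechanism first and prefers predictive only over prognostic. Baseline PAR (1.3.3), germline polymorphisms (8.8) and the BRCAPro score (8.12) also serve that aim.

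Fourth, the inflated rejection rates need a correlation with prognosis in one arm and none in the other. With equal correlation there is no inflation beyond the null cells. This also stands: the range is illustrative, not an expected error rate.

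Exploratory status limits the stakes. It does not make a post-treatment change able to answer a question about effect modification.

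**Conclusion.** The point holds in limited form. On either reading of predictive, relating a day-3 change to PFS or response supports only a pharmacodynamic or prognostic conclusion; it cannot identify patients who benefit from adding cediranib. If an arm-by-change interaction were used, it could be spurious: about 11-48% rejection at 0.05 for 40-82 patients under the one-arm correlations of the first simulation, and up to 58% under the strongest setting of the second, against about 6-7% when the correlation is equal or absent. Those figures rest on assumed correlations and subset sizes, and 82 would require every evaluable patient to opt in.

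The matter is confined to exploratory objectives. The primary PFS comparison and the futility look in section 14.2 do not use these markers. A reader might also think it serious that PFS starts at treatment (section 10.4.5), before the day-3 value exists. With scans every 8 weeks the effect of a three-day gap is negligible, so a landmark is optional.

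**What to change.** In sections 1.3.3 and 8.2, for these exploratory objectives only:

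- Address the predictive question with the pre-treatment values of Ktrans and kep, cytokines and CEC, through a marker-by-arm interaction: a Cox model for PFS and a logistic model for response.
- Compare day-3 changes between arms as pharmacodynamic outcomes. The cytokine objective already asks for this in part.
- Report any link between day-3 change and PFS or response within arm, as a pharmacodynamic or prognostic association, and do not call it predictive.

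The cost is wording and a choice of model. No new samples or visits are needed, because the pre-treatment measurements are already scheduled. The downside is that baseline-by-arm interactions will be imprecise in an optional subset of at most 90 randomised patients, and fewer predictive claims will be possible.
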